Suicide Risk Management Plan

The rater who will be conducting C-SSRS has a master's degree in clinical psychology and has many years of experience working with vulnerable clinical patients. The rater has been administering C- SSRS under other protocols for the past two years. The C-SSRS will be conducted every week of the four-week study. In addition, the study PI (MD/PhD) will conduct a rigorous assessment with participants prior to the start of treatment, including asking if they have suicidal thoughts and plans, which will be recorded on the evaluation note form in the redcap. After the screening session, the study PI and the rater will go through the inclusion/exclusion criteria together to determine the patient's eligibility. On each day of the 10-day treatment, a covering MD will ask a series of questions about the patient's symptoms, mood, suicidal thoughts and medication use before starting the session. These will be recorded in the progress note form on the redcap after each day of treatment. All research members involved in the study have completed all necessary CITI training courses to ensure the safety and welfare of participants.

The rater will gather lifetime history of suicidality as well as any recent suicidal ideation and

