Recruitment Procedures

Recruitment of adults with schizophrenia or schizoaffective disorder from the study "Study of Early Cortical Processing in Schizophrenia" (Protocol #7114) within the Division of Experimental Therapeutics at NYSPI.

Potential participants will also be recruited through flyers and online advertisements posted on Craigslist, Facebook, and RecruitMe.

Research staff from the "Study of Early Cortical Processing in Schizophrenia" (Protocol #7114) will tell adult patients with schizophrenia or schizoaffective disorder about the study and ask if they would like to meet with investigators or research staff of this "A pilot open-label trial of individualized repetitive transcranial magnetic stimulation for patients with auditory verbal hallucinations" to learn more about the study and have any questions answered. For patients who express willingness to be contacted, the investigators and/or coordinators of the "Study of Early Cortical Processing in Schizophrenia" (Protocol #7114) will pass contact information along to appropriate research staff of the present protocol. A member of our research staff will send a targeted recruitment email and/or call the participants who express interest. Patients will also be recruited through flyers, Craigslist and online postings to recruitment websites.

Inclusion/Exclusion Criteria

Our criteria for the subject population are based on previously approved protocols of HD-tDCS on schizophrenia and schizoaffective patients led by [name] (IRB # 7882), previous trials on TMS in treating AVH (Auditory Verbal Hallucinations) in patients with schizophrenia (Hoffman et al., 2005; Thomas et al., 2019), and the FDA guidance on TMS (https://www.fda.gov/medical-devices/guidance-d-radiation-emitting-products/repetitive-transcranial-magnetic-stimulation-rtms-systems-class-ii-special-controls-guidance).

Inclusion

Criterion	Method of Ascertainment		
1. Age between 22-55	Self-report		
2. DSM-V diagnosis of schizophrenia or schizoaffective disorder	Structured Clinical Interview for DSM-5		
3. Capacity and willingness to provide informed consent	Independent assessment of capacity		
4. Mean AHRS item score of greater or equal to 2.	Auditory Hallucinations Rating Scale (AHRS)		

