We will recruit participants from NYSPI # 7114 (Study of Early Cortical Processing in Schizophrenia). In order to better understand the burden to participants who enroll in both protocol #7114 and the current protocol, we are summarizing the study procedures in # 7114: After providing informed consent, participants undergo a 2 hours phone screen (such as the SCID) to confirm diagnosis and assess comorbidity. Participants then partake in a 9-hour in person behavioral session (across two visits) that involves IQ tests, neurophysiological evaluation, collection of speech samples, and behavioral tests such as basic sensory, emotion recognition and reading tasks. Participants then undergo EEG sessions (8 hours), which can be done across 1-2 visits as best accommodates participants' schedules. There are also 2 hours of MRI acquisition. Before going into the MRI scanner, all participants are screened using the NYSPI MRI safety questionnaire re metal implants. Women have urine pregnancy tests. #7114 is a cross-sectional study of deficits in early cortical or basic sensory processing, across stages of schizophrenia and related psychotic disorders and autism spectrum disorder (ASD). Participants in the protocol #7114 include patients (schizophrenia, recent-onset psychosis, clinical high risk and autism spectrum disorder) and for comparison, healthy volunteers similar in demographics. We will only recruit schizophrenia patients from the protocol #7114.

The total participation period for each subject in this pilot study is 4 weeks, starting at week 0 and ending at week 3.

Procedure Table:					
Week	0	1	2	3	
Activity	Consent, screening, audiometry, pre- treatment baseline assessments:AHRS (audiotaped), PSYRATS,SAPS, PANSS, CAPS,EEG tasks, fMRI	C-SSRS (weekly); CGI-S and CGI-I (daily; before treatment session); SAFTEE (daily; before treatment session) 5-day 1x/day treatment (5 sessions)	C-SSRS (weekly); CGI-S and CGI-I (daily; before treatment session); SAFTEE (daily; before treatment session) 5-day 1x/day treatment (5 sessions)	C-SSRS Audiometry, post- treatment assessments: AHRS(audiot aped), PSYRATS,SA PS, PANSS, CAPS, EEG tasks, fMRI	

Screening/Informed Consent:

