Informed consent will be obtained before any study procedures are initiated. After providing informed consent, subjects will undergo medical screening (medical history, physical examination, vital signs, urine pregnancy test for women of childbearing potential, psychiatric screening (i.e. Structured Clinical Interview for DSM 5 (SCID) (Dunn et al., 2002), Auditory Hallucination Rating Scale (AHRS) (Hoffman et.al, 2003), Columbia Suicide Severity Scale (C-SSRS) (Posner et al., 2007), Transcranial Magnetic Stimulation Adult Safety Screen (TASS) (Keel et.al., 2001) and audiometry to confirm eligibility. Screening procedures (except for physical exam) may be conducted by an RA trained by the Principal Investigator; consent procedures must be conducted by an MD. A study MD ([name]/PhD) or [name]/PhD) will be available to answer questions, if a subject wishes to speak to a doctor about the risks/benefits of TMS.

Evaluation and motor threshold assessment

Clinical and medical screening includes a physical exam and history, vital signs, review of inclusion and exclusion criteria, and urine pregnancy test (for women). Participants will then have an assessment of resting motor threshold (RMT; 1 minutes). This procedure is described, in detail, below. This session will last about 1 hour.

EEG sessions:

EEG tasks related to AVH will be compared pre/post treatment. There are ~5 hours of EEG recording, which will be done across 2 visits at baseline and post treatment. Each EEG session is expected to last 2.5 hours (1 hour of setup + 1.5 hours of tasks). EEG will be acquired on a 64-channel, active-electrode Brainvision system, digitized at 500 Hz. RAs with EEG data collection experience will conduct this session. All tasks involve listening to sounds via headphones or speakers and some tasks require behavioral responses via button presses or mouse clicks. In some cases subjects are also instructed to view a fixation cross on a monitor or perform a basic visual task while listening to sounds.

MRI (structural MRI, task-related and resting-state functional MRI):

There are ~4 hours of MRI acquisition, which will be done across 2 visits at baseline and post treatment. Each MRI session will include anatomical scans, resting-state fMRI, and an auditory fMRI task. The participant will be placed in a supine position on the table. A head-holder will be used to decrease head movement during the scan. Participants will be given a squeeze ball which

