Clinical assessments include Auditory Hallucination Rating Scale (AHRS), the Psychotic Symptom Rating Scales (PSYRATS), the Scale for the Assessment of Positive Symptoms (SAPS), the Positive and Negative Symptoms Scale (PANSS) and the Cardiff Anomalous Perceptions Scale (CAPS). These clinical assessments involve answering questions about psychiatric symptoms. The total assessment time will take up to 1 hour 40 minutes. There will be baseline (week 0) and post-treatment (week 3) assessments. These assessments will be conducted by RAs who have completed training for each measure used. The Clinical Global Impression Scale (CGI-S and CGI-I) will be completed by [name] or other clinically trained personnel before each treatment session to quantify and track participant progress and treatment response over time, based on the above measures and general clinical impressions. AHRS assessment will be audiotaped. The second clinical rater will listen to an audiotaped session, blind to subject identity and session number. In addition, [name] or other clinically trained personnel will ask participants questions using the Systematic Assessment for Treatment of Emergent Events (SAFTEE), and this will be done once on each treatment day. The Columbia Suicide Severity Rating Scale (C-SSRS) will be conducted by a qualified clinician (e.g., physician, licensed clinical psychologist, psychiatric nurse practitioner, licensed clinical social worker, or other qualified mental health clinicians).

Participants will be administered the C-SSRS weekly to ensure that they meet the study safety/eligibility requirements. The study PI will be informed and will assess the participant for suicidality and safety. The PI will contact the participant's primary mental health provider to inform them of patient's current level of suicidality. If the PI determines that the participant is an immediate risk/danger to themselves or others, or feels that an emergency evaluation is clinically indicated, the patient will be referred the emergency room at CUMC/NYP-Columbia.

TMS Sessions:

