De-identified data may also be shared with other investigators at NYSPI for the purposes of substitution in the case of failure of data collection. For instance, if the subject participates in another MRI protocol at NYSPI, and during those sessions the investigators fail to collect all of the needed anatomical and functional MRI sequences, we may share our data with them if we have collected the same types of MRI sequences for our protocol. The inverse may happen as well; we may receive data from another NYSPI protocol if because of a technical failure we are unable to collect all of the necessary MRI sequences.

Direct Benefits to Subjects

Participants may not experience any direct benefits from their involvement in this study.

The proposed project is a clinical trial of TMS for treatment of AVH and an experimental intervention. Therefore, we do not consider AVH treatment a definite benefit of participation. Nevertheless, participants are informed of the purpose of the trial and may in fact experience a reduction in AVH.

MRI findings and clinical assessments are unlikely to be of direct benefit to participants, but subjects will be informed of any clinically significant findings from the MRI and clinical assessments.

Compensation and/or Reimbursement

Subjects will be compensated as follows:

- Pre-treatment session (screening, clinical assessment, EEG and MRI): \$185
- Treatment day: \$100
- Post-treatment session (clinical assessment, EEG and MRI): \$160

In this study, each subject will undergo 1 pre-treatment session, 1 post-treatment session and 10 treatment days. Total compensation for all sessions is \$1345.

Statistical Analysis Plan

We will use a repeated measures t-test to analyze changes in the Auditory Hallucination Rating Scale (AHRS). This involves comparing scores before and after TMS treatment in participants who completed all study procedures. The goal of this analysis is to determine if there are improvements in symptoms of auditory verbal hallucination. Additionally, similar analyses will be performed for secondary outcome measures such as PANSS, investigating if there is a significant decrease in PANSS P3 scores for participants after the TMS treatment sessions.

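### Does using AHRS as both the entry cut-off and the pre/post outcome call for a separate, later baseline reading?

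*Combined protocol and SAP*

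**What the plan says.** AHRS has two roles. Under Inclusion/Exclusion Criteria it is an entry threshold: "4. Mean AHRS item score of greater or equal to 2". Under Screening/Informed Consent it belongs to a battery that ends "and audiometry to confirm eligibility". In the Statistical Analysis Plan, AHRS change is tested with a paired t-test: "This involves comparing scores before and after TMS treatment in participants who completed all study procedures". There is one arm.

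On timing, the week-0 cell of the Procedure Table lists consent, screening and audiometry, and then pre-treatment "baseline assessments:AHRS (audiotaped), PSYRATS,SAPS, PANSS, CAPS,EEG tasks, fMRI". The Assessments section says "There will be baseline (week 0) and post-treatment (week 3) assessments". The Suicide Risk Management Plan describes a distinct step: "After the screening session, the study PI and the rater will go through the inclusion/exclusion criteria together to determine the patient's eligibility". The compensation section groups the work as "Pre-treatment session (screening, clinical assessment, EEG and MRI") and says that "each subject will undergo 1 pre-treatment session, 1 post-treatment session and 10 treatment days".

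No sentence states whether AHRS is taken once or twice before treatment, or which reading the t-test uses.

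**The concern.** Patients admitted because they scored above a cut-off on a fluctuating scale include some who were having a bad day. Measured again, the group mean is expected to fall even if treatment does nothing. With no control arm, that fall counts as improvement. The Lay Summary makes a promising reduction in hallucinations the ground for a larger sham-controlled trial, so the bias favours going ahead.

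The documents give some reason to suspect a shared reading. The week-0 cell itemises AHRS once, and the payment text places screening and clinical assessment in one pre-treatment session. A reader could conclude that the eligibility score is the baseline and that the plan should require a second, later reading to which no threshold applies.

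**Working it through.** The plan states no power, SD or reliability, so there is no figure of its own to reproduce.

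**1. Which reading is the baseline?**
- If AHRS is taken once in week 0, the pre-treatment score is unambiguous and regression to the mean applies in full.
- If it is taken twice, the reading labelled baseline and audiotaped in the Procedure Table is the obvious choice, and the bias may be smaller.
- The single pre-treatment session is a payment line and weak evidence of one sitting. The stated week-0 durations are about 1 hour of evaluation, 2.5 hours of EEG, half of about 4 hours of MRI, and up to 1 hour 40 minutes of scales: 60 + 150 + 120 + 100 = 430 minutes, a little over 7 hours.

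Either way an analyst knows which score to use. The documents do not establish that it is the eligibility reading.

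**2. Size if it is the eligibility reading**

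From the documents: 12 enrolled and 10 completers (Description of Subject Population). Assumed: normal scores, retest correlation r of 0.6 to 0.9, two-sided 5% level. If the 12 are counted at consent, at most 2 can fail the cut-off.

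Expected fall with no effect, in SDs of the unselected AHRS: (1 − r) × λ, where λ = φ(c)/(1 − Φ(c)) and c is the cut-off in SD units.
- 2 of 12 fail: c = −0.967, λ = 0.300. The fall is 0.1 × 0.300 = 0.030 at r = 0.9 and 0.4 × 0.300 = 0.120 at r = 0.6.
- 1 of 12 fails: c = −1.383, λ = 0.167. The fall is 0.017 to 0.067.

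Precision at n = 10 with 2 of 12 failing: the variance of the eligibility score after selection is 1 + cλ − λ² = 0.620. The variance of change is (1 − r)² × 0.620 + (1 − r²), which is 0.739 at r = 0.6 and 0.196 at r = 0.9. The 95% half-width is 2.262 × SD of change/√10, or 0.615 and 0.317 SD. The bias is therefore 0.120/0.615 = 19.5% and 0.030/0.317 = 9.5% of it.

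Simulated error rates under no effect:

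| Share failing | False significant improvement (nominal 2.5%) | Total two-sided error (nominal 5%) |
|---|---|---|
| 1 of 12 | 3.2% to 4.0% | 5.2% to 5.5% |
| 2 of 12 | 3.9% to 5.8% | 5.4% to 6.7% |

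If the 12 are counted after eligibility, the share failing is not given. At 30% failing the fall is 0.05 to 0.20 SD with two-sided error of 6.4% to 10.1%. At 50% it is 0.08 to 0.32 SD with 8.1% to 18.9%.

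**3. What a later baseline would gain**

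Let 1, 2 and 3 be the screening, later-baseline and week-3 readings. With reading 2 as baseline the fall is (r12 − r13) × λ, so the share of bias remaining is (r12 − r13)/(1 − r13). With r13 = 0.6:
- r12 = 0.6: none remains. The half-width becomes 2.262 × √0.8/√10 = 0.64 instead of 0.615 SD, about 4% wider.
- r12 = 0.7: 0.1/0.4 = one quarter remains.
- r12 = 0.8: 0.2/0.4 = one half remains (0.06 SD).
- r12 = 0.9: 0.3/0.4 = three quarters remains (0.09 SD).

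Readings taken closer together usually correlate more, so full removal is the optimistic case.

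**The case for a change.** The strongest case for a change is that calling the bias small is itself an assumption. Neither reliability nor the failing share is documented, and if half the candidates failed the cut-off the bias would matter. The blinded tape rating does not help, because it addresses rater expectation and not real fluctuation on the qualifying day. A stable antipsychotic dose for four weeks does not remove fluctuation either. Naming the baseline would take one sentence, and a reading on treatment day 1 would need no extra visit.

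Much of this stands. The direction of the bias is right, its size cannot be confirmed, and a write-up should name regression to the mean among the limits of an uncontrolled change. Heavy truncation is less likely, though: the Background describes participants with persistent hallucinations, and candidates review the criteria before consenting. Even 2 of 12 is an extreme when the 12 are counted at consent, since it leaves no loss for dropout or any other reason.

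The day-1 reading also has costs. It adds a taped interview, for which the protocol itself lists boredom and fatigue as risks. It also moves the AHRS baseline away from the week-0 EEG and fMRI baselines, while Aim 2 relates change in hallucination severity to change in those measures.

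**Conclusion.** No change is needed. A minimum severity on the target symptom is an ordinary entry rule, and the missing sentence on the baseline is a gap that an analyst fills sensibly with the audiotaped week-0 baseline AHRS. If that is also the eligibility reading, the bias towards improvement is about 0.02 to 0.12 SD. This assumes normal scores, 1 or 2 of 12 below the cut-off and a retest correlation of 0.6 to 0.9; heavier truncation, which the documents do not suggest, would enlarge it.

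An added baseline reading is a trade-off on which statisticians could differ: a partial reduction of a probably small bias, against an extra assessment and less well-aligned baselines for Aim 2. It would alter no stated decision, because the plan sets no significance level or numerical go rule. The pilot is openly uncontrolled, and in the sham-controlled trial meant to follow, regression to the mean would be expected equally in both arms.

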Headache is the most common side effect of TMS. This headache is typically of a muscletension type. It usually develops during or immediately after the stimulation and may last for minutes to hours following the end of the stimulation. It is typically limited to the day of stimulation, and usually responds promptly to single doses of over the counter pain medications. TMS can also stimulate scalp muscles and produce a twitch in the scalp or upper face that can be uncomfortable for some, painful for others. Neck pain can occur related to head immobilization, and trigeminal stimulation can also lead to a sense of discomfort. Scalp pain may also occur. Migraine has not been reported with TMS. Pain, headache and discomfort, while uncomfortable, do not indicate any problems with safety, and are easily managed with over-the-counter analgesics.

According to Rossi et al., 2009, in therapeutic TMS, 28% of patients experience headache and 39% experience pain or discomfort (vs. 16% and 15% respectively with sham TMS). In prior clinical studies at NYSPI of daily therapeutic TMS for up to 10 days in depressed patients, the frequency of headache with active TMS did not differ from sham (also ~28%). In clinical trials, <2% of patients discontinue TMS because of pain.

In the majority of cases, any pain related to TMS rapidly vanishes with the cessation of TMS, though headaches may occasionally persist, such that an oral analgesic is indicated.

Cognitive changes

In general, the effects of TMS on cognition are relatively low, in both healthy and patient populations. Fitzgerald et al. (2005) reported the effects of low frequency rTMS in patients with treatment-resistant auditory hallucinations, without significant deterioration in any cognitive test. Per Rossi et al., 2020, to date no reliable evidence has indicated longer lasting side effects of TMS on cognition.

Acute psychiatric changes

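### SAFTEE stops before the last rTMS session and is not repeated at week 3, so general adverse events that begin after that session get no structured enquiry

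*Combined protocol and SAP*

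**What the plan says.** In the Procedure Table (Study Procedures), the cells for weeks 1 and 2 carry "CGI-S and CGI-I (daily; before treatment session); SAFTEE (daily; before treatment session". The week-3 cell reads "C-SSRS Audiometry, post- treatment assessments: AHRS(audiot aped), PSYRATS,SA PS, PANSS, CAPS, EEG tasks, fMRI"; CGI and SAFTEE are not in it.

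The Assessments section agrees. For the five symptom scales it states "There will be baseline (week 0) and post-treatment (week 3) assessments". It describes CGI and SAFTEE separately. CGI is rated before each session, "to quantify and track participant progress and treatment response over time, based on the above measures and general clinical impressions". SAFTEE is introduced with "Systematic Assessment for Treatment of Emergent Events (SAFTEE), and this will be done once on each treatment day".

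Four other places bear on the point:
- Local pain, headache, discomfort says of headache, named there as the commonest side effect: "It usually develops during or immediately after the stimulation and may last for minutes to hours following the end of the stimulation".
- Protections Against Risk (item 5) has adverse events documented in the treatment notes. It promises severity, duration, any intervention and whether the event resolved, for each event.
- Suicide Risk Management Plan gives the covering physician a daily set of questions, also before the session and on treatment days only.
- Study Procedures ends participation at week 3.

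**The concern.** An enquiry made before a session can pick up events from previous sessions, but not from the one about to start. Sessions 1 to 9 are each followed by another enquiry; session 10 is not. The protocol itself expects its commonest side effect to start during or just after stimulation and possibly to last for hours, so the window left open is one where events are expected.

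At stake is the completeness of the safety record. The pilot is meant to prepare a larger sham-controlled trial, and with 10 completers one or two unrecorded events would visibly change any tolerability rate drawn from it. The commitment to record duration and resolution is also hard to keep for events from the last session if nobody is scheduled to ask.

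CGI has the same schedule. It is said to rest partly on scales that are measured only at weeks 0 and 3, yet it is not rated at week 3, the one post-treatment visit where they are available.

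**Working it through.** **Reproducing the plan's exposure figures.** Inputs are from the Procedure Table and the section on repetitive TMS.
- Sessions: 5 (week 1) + 5 (week 2) = 10, as stated.
- Pulses per session: 20 min × 60 s × 1 per second = 1,200, as stated.
- Total pulses: 10 × 1,200 = 12,000, as stated.

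**Exposure before the last SAFTEE.** If *n* sessions are given and SAFTEE precedes each, the last one follows *n* − 1 sessions, a share of (*n* − 1)/*n*. A course with at most two missed days still counts as complete, so *n* runs from 8 to 10 among completers.

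| Sessions given | Sessions before last SAFTEE | Pulses before last SAFTEE | Share |
|---|---|---|---|
| 10 | 9 | 9 × 1,200 = 10,800 of 12,000 | 90% |
| 8 | 7 | 7 × 1,200 = 8,400 of 9,600 | 87.5% |

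With a week-3 SAFTEE the share is 100% in both rows.

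**Scheduled coverage after the last session, by domain.**

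| Domain | Week-3 assessment |
|---|---|
| Suicidality | C-SSRS |
| Hearing | Audiometry; the Hearing section requires any change to be reported as an adverse event |
| Psychotic symptoms | AHRS, PSYRATS, SAPS, PANSS, CAPS |
| Other events, mainly somatic (headache, scalp or neck pain) | None scheduled; treatment notes and volunteered reports only |

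**Does it matter whether SAFTEE is before or after the session?** The table says before. The Assessments text says only "this will be done once on each treatment day", which would allow it afterwards on the same day. On that looser reading, events that begin once the participant has gone home from the last session are still not asked about, and neither is resolution. The point survives, with a shorter window.

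**The case against.** A reader might infer that nothing checks safety after session 10. The documents do not support that. C-SSRS, audiometry and the psychosis scales are all scheduled at week 3. Staff monitor the whole of every session, participants are encouraged to report discomfort, and events go into the treatment notes. Headache that starts during or immediately after stimulation would often begin while staff are present. This stands, and it narrows the gap to structured enquiry about general events with later onset, and about resolution.

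A reader might also take the tenth session as meaning that 10% of adverse events are lost. That would need events spread evenly over sessions and no other means of capture, and the second condition is false. A rough illustration shows how small the numbers are. Take the 28% headache figure quoted in the protocol as a per-participant incidence, and assume that first onset is equally likely at each of 10 sessions. Then 10 completers × 0.28 × 1/10 = 0.28 participants would have a first headache at session 10, before allowing for on-site observation. This counts first headaches only, not repeat headaches or other events.

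Third, the Statistical Analysis Plan defines no tolerability endpoint and mentions no adverse-event table, so it is too strong to say that a planned result is biased. That is correct. What is affected is the completeness of the safety data from which any later summary would be drawn.

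Finally, the one decision that uses CGI is the on-treatment trigger in Criteria for Early Discontinuation. A daily pre-session rating serves it, and after session 10 there is no treatment left to stop. CGI is not an outcome in the Statistical Analysis Plan, and response to the full course is measured by the week-3 scales. This stands too and makes the CGI part secondary. It does not answer the SAFTEE part: no other scheduled assessment asks about general events after the last session.

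**Conclusion.** The point holds for SAFTEE. Table and text agree that it is confined to treatment days, and nothing else in the documents schedules a general adverse-event enquiry after the last session. In size, the last SAFTEE follows 90% of the pulses in a full course and 87.5% in an eight-session course. The documents give no basis for turning these shares into a count of missed events, and that count is probably small with 10 completers.

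It would go too far to infer that safety follow-up is absent or that the efficacy analysis is weakened. Three safety-relevant domains are covered at week 3, and the comparisons of AHRS and PANSS P3 use neither SAFTEE nor CGI. The absence of a week-3 CGI sits awkwardly with its stated purpose of tracking response, but it is a descriptive matter only.

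This rests on reading the Procedure Table as complete for week 3, which the Assessments section supports. It is a low-cost improvement worth making, not a flaw that threatens the trial's conclusions.

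**What to change.** 1. Add SAFTEE to the week-3 column of the Procedure Table and to the Assessments text. Have it cover the period since the last pre-session enquiry, including whether events from the last session have resolved.
2. State that the week-3 SAFTEE is included whenever adverse events are summarised. The Statistical Analysis Plan does not currently mention such a summary, so one sentence is needed there.
3. Optionally, rate CGI-S and CGI-I at the same visit, state the reference rating for CGI-I, and report them descriptively without adding an outcome test.

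The cost is a few minutes at an existing visit. The Assessments section gives the week-3 symptom scales to research assistants but SAFTEE and CGI to clinically trained staff, so such a person must be available. C-SSRS already brings a qualified clinician into that week, but the documents do not say whether the same person may complete SAFTEE or CGI. That should be settled. Treatment, eligibility and the planned analyses of AHRS and PANSS P3 do not change.
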